Exclusion Criteria: Study candidates with the following will be excluded: 1) known genitourinary pathology beyond neuropathic bladder (i.e., vesicoureteral reflux, bladder or kidney stones, etc.); 2) use of prophylactic antibiotics; 3) instillation of intravesicular agents to reduce UTI (i.e., gentamycin); 4) psychologic or psychiatric conditions influencing the ability to follow instructions; 5) participation in another study in which results would be confounded; 6) pregnant or breastfeeding; 7) individuals with a history of acquired or genetic immunodeficiencies; active, acute or chronic serious infections (i.g., viral hepatitis, HIV/AIDs); 8) individuals with cancer/autoimmune disorders; 9) serious allergy to any component or excipients in the live bacterial combination product; 10) no change in neurologic status in the previous 2 weeks; 11) taken antibiotic for any reason in the previous 2 weeks; 12) any patient with history of sensitivity or allergy to ampicillin or tetracycline; and 13) current urinary tract infection or urinary tract infection within the previous 2 weeks (as defined by Infectious Diseases Society of America CAUTI Guidelines, 2010. According to the Infectious Disease Society of America Guidelines for Diagnosis of Catheter-Associated UTI, the presence of the following urinary symptoms is required for UTI diagnosis in patients using intermittent catheterization: new onset or worsening fever, rigors, altered mental status, malaise, lethargy with no other identified cause, flank pain, costovertebral angle tenderness, acute hematuria, pelvic discomfort, increased spasticity, autonomic dysreflexia or sense of unease. The Guidelines specifically state that “the presence or absence of odorous or cloudy urine should NOT be used as an indication for urine culture or antimicrobial therapy” and “the presence, absence or degree of pyuria should NOT be interpreted as an indication for antimicrobial treatment.” If a subject presents with any of these symptoms and there are $\geq 10^3$ cfu/hpf bacterial growth on urine culture, the subject will be excluded and treated for a UTI according to clinical best practice.

Baseline Data Collection: After consent, participants will complete the Health History Questionnaire. Thereafter, participants will complete the Urinary Symptom Questionnaire (USQ-NB) weekly.

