Intervention: After 6 months of baseline data collection, participants will receive the *Lactobacillus* (Culturelle) kits. Participants will be instructed on preparation and intravesicular instillation of the *Lactobacillus*, and will have a tutorial with a fellow consumer on use of the patient-initiated SMP_{PRO}. Participants will receive 10 Culturelle tablets the beginning of the

The Impact of Self-Management with Probiotics on Urinary Symptoms and the Urine Microbiome in Individuals with Spinal Cord Injury and Spina Bifida Protocol

5/18/2017

Page 5 of 17

treatment phase. At the end of each week, the coordinator or RA will ask how many remaining tablets the participant has and will instruct them to complete the USQ-NB weekly. If/when urinary symptoms occur, they will be instructed to follow the SMP_{PRO} protocol to determine whether to initiate intravesicular *Lactobacillus* instillation or to seek medical attention. The self-management protocol will also direct them to discontinue *Lactobacillus* instillation or to seek medical attention if symptoms remit, persist or worsen. If participants are directed by the self-management protocol to seek medical attention or s/he feels the need for medical evaluation, s/he will be advised to obtain care as they typically would by their health care provider. Participants will be supplied with letters to be brought to their health care provider notifying them of the study and requesting sharing of urinalysis and urine culture results with the research team. A verified UTI will include those that resulted in antibiotic treatment prescribed by a health care professional.

For the intravesicular *Lactobacillus* instillation, the contents of 1 *Lactobacillus* capsule will be mixed into 45 cc sterile 0.9% saline (adult bladder volume is 450cc, representing 10% of adult bladder volume). After mixing, study participants will draw up the 45 cc of the liquid *Lactobacillus* mixture into a 60cc catheter tip syringe and instill via the intermittent catheter using sterile technique. For children volume is based on age (see table on page 4 of protocol).

Study participant will recheck symptoms after 24 hrs (valid range 22-30 hrs) following the SMP_{PRO} protocol and either perform another *Lactobacillus* instillation or seek medical attention, per the subjects choice. If symptoms still persist 4 hrs after second instillation, study participants are instructed to seek medical attention.

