Post-Intervention Follow-Up: After completion of the 6-month patient-initiated self-management protocol intervention period, participants will monitor symptoms weekly using the USQ-NB.

Measurements:

Health History Questionnaire: After subjects give consent, a brief medical history will be conducted using a structured questionnaire, to obtain demographic information and relevant family history (these items will be collected only at baseline), and genitourinary history

Urinary Symptom Questionnaire (USQ-NB): A preliminary urinary symptom questionnaire has been developed with consumer input based on the most common typical and SCI/MS-specific urinary symptoms. The final version (developed in Specific Aim 1 IRB # 2014-187) will be used in this phase of the study. USQ-NB will be completed weekly. All participants will receive a link to the questionnaire every Sunday morning. If they have not responded by Monday morning, they will receive another link. If they have not responded by Tuesday, the study participant will receive a phone call. If there is no response by noon Wednesday, it is considered a missed event.

Patient satisfaction: We have developed a simple four item patient satisfaction “survey” that will be requested at the end of each timeframe. Participants will be asked to rate their satisfaction, thinking only about the preceding time period, with changes in the *frequency* of their symptoms; the amelioration of the *severity* of their symptoms; and changes in the *impact* of their symptoms. A 5-point Likert scale will be used for each of these items (not at all satisfied; not very satisfied; no perceived difference; satisfied; and very satisfied). A fourth item, “Can you estimate, using a scale from 0% <would absolutely never do this>, through 50% <might do this> to 100% <would absolutely always do this>, whether or not you would seek this intervention out and pay for it yourself if insurance did not pay for it”.

Medical Information:

The Impact of Self-Management with Probiotics on Urinary Symptoms and the Urine Microbiome in Individuals with Spinal Cord Injury and Spina Bifida Protocol

5/18/2017

Page 6 of 17

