If participants instill *Lactobacillus* at any time during the intervention phase, and after *Lactobacillus* instillation reports a UTI as an Adverse Event (AE) we will request their urinalysis and urine culture results to attempt to determine if *Lactobacillus* might have been the cause of the UTI. If determined necessary by the PI, Co-PI and/or DSMB other AEs reported could require retrieval of medical records.

Phase III: Pilot Study of Multiple (up to 2) *Lactobacillus* Bladder Instillations

We will recruit 30 persons in whom we will collect urine up to 18 timepoints (up to monthly for the first year when not experiencing symptoms, up to two times when subject experience urinary symptoms, follow-up after either *Lactobacillus* treatment or antibiotics, and three (3) months into the six (6) months follow-up) in order to **estimate the strength of the associations between successful implementation of the probiotic self-management program and urinary symptoms, bladder inflammation, and the urine microbiome.** We will conduct an 18-month study in which each participant will serve as his/her own control through 3 phases of study: 6-months usual care (baseline), 6-months probiotic intervention, and 6-months follow-up
Study Design: We will recruit N=30 subjects with neuropathic bladder who will contribute urine samples for analyses.

Clinical Setting: MedStar National Rehabilitation Hospital and Children's National Medical Center.

Target Enrollment: 30 adult subjects at least 1-year post-injury and 18 years of age with SCI/MS or at least 18 years of age with SB

Recruitment Strategy: SCI/MS and SB subjects will be enrolled with assistance from United Spinal Association. Additionally, we will query the MedStar National Rehabilitation Hospital inpatient service, the 40+ MedStar National Rehabilitation Network outpatient sites, various MedStar Network databases, and the CNMC Spina Bifida database. Databases will be queried for participants who meet the eligibility criteria and have already provided HIPAA authorization and consent to be contacted for future research. Announcements and IRB-approved flyers will be posted on the United Spinal Association and study websites and at participating institutions.

Informed Consent: Consent will be obtained by the PI, Study Coordinator, or Research Assistant. All project staff are currently CITI certified and have passed all requirements for HIPAA certifications.

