H1. Compared with usual management, self-management of urinary symptoms with probiotics will reduce the frequency, severity and impact of urinary symptoms and UTIs (PRIMARY OUTCOMES). The goal of aim 2 is to assess the effect of *Lactobacillus* supplementation on the frequency, severity and impact of urinary symptoms and UTIs. This aim can be evaluated with all 100 participants in the SMP pilot study. We expect to find a significant difference in these primary outcomes between our three experimental timeframes (6 months prior to intervention, 6 months of SMP_{PRO} intervention, and 6 month follow-up period). Frequency of UTI will be defined as the number of verified UTIs occurring during the timeframe. Urinary symptoms will be assessed using the USQ-NB where frequency of symptoms, degree of severity, and impact on the individual, will be considered.

We will estimate the average number of symptoms on the USQ-NB endorsed (irrespective of frequency, severity and impact) across the weeks during that time frame, for each participant. Thus, each participant will have a continuous outcome (average number of USQ-NB items endorsed). We will also compute the number of verified UTIs experienced by each participant. These two outcomes are the primary outcomes for our study and analysis; they depend solely on the face validity of the USQ-NB, and on clinically verified UTIs, and so will not be affected by a failure to find or establish formal measurement properties for the USQ-NB, should any occur. They will also be less subject to any variability in participant perceptions of frequency, severity or impact, which can complicate analytic assumptions and limit power and interpretability of change that might be perceived. We will describe these features of the sample over time but will not conduct inference tests on these ratings.

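### The plan gives no common method for capturing verified UTIs across the three periods it compares, so equal ascertainment of this co-primary count is not assured

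*Combined protocol and SAP*

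**What the plan says.** Under H1 the UTI outcome is defined so: "Frequency of UTI will be defined as the number of verified UTIs occurring during the timeframe". The timeframes are 6 months of usual care, 6 months of the self-management protocol with probiotic, and 6 months of follow-up. Each participant is his or her own control.

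The meaning of a verified UTI is given in the Phase II Intervention text: "A verified UTI will include those that resulted in antibiotic treatment prescribed by a health care professional". The Phase III intervention text repeats it almost unchanged.

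The procedures written for each Phase II period are these:

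- **Baseline Data Collection:** a health history questionnaire after consent, and then "Thereafter, participants will complete the Urinary Symptom Questionnaire (USQ-NB) weekly".
- **Intervention:** "Participants will be supplied with letters to be brought to their health care provider notifying them of the study". The letters also ask the provider to share urinalysis and culture results. In addition, "At the end of each week, the coordinator or RA will ask how many remaining tablets the participant has", with an instruction to complete the USQ-NB. The Phase III intervention text has the same letters.
- **Medical Information:** if a participant who has instilled during the intervention phase later reports a UTI as an adverse event, "we will request their urinalysis and urine culture results".
- **Post-Intervention Follow-Up:** "participants will monitor symptoms weekly using the USQ-NB".

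Three provisions are not tied to one period. The introductory section on Specific Aim 2 lists records of UTIs among the pilot data. The USQ-NB paragraph under Measurements sets out a weekly link and a reminder, and then: "If they have not responded by Tuesday, the study participant will receive a phone call". H3 takes antibiotic use from medical records or self-report and analyses it over the same three periods.

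**The concern.** The UTI analysis is a before/after comparison in the same people. No concurrent group would share a change in how events are found, and the mixed model under H1 cannot separate a change in capture from a change in UTI rate, because both coincide with period. The count therefore needs the same capture method in every period.

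The plan describes provider notification and weekly staff contact in one period only. It describes no route by which an antibiotic prescription for UTI reaches the study team in the other two. Sites that follow the text as written could learn of UTIs more readily in one period than in another. A baseline event that is not recorded when it occurs cannot be reliably recovered later.

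The bias could go either way. Better capture during the intervention than at baseline would hide a benefit. Poorer capture in follow-up, once the weekly contact stops, would look like a sustained benefit, and whether the change persists after the intervention is something the H1 analysis sets out to assess.

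**Working it through.** **Inputs from the Power calculation paragraph:** n = 100; mean UTIs 6 at baseline and 4.75 during the intervention, a difference of 1.25; SD 4; alpha 0.025 per co-primary outcome; stated power 81%.

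**Assumptions, because the documents are silent:** the test is two-sided; the SD of 4 is that of the within-person change (the plan calls it the SD of the number of UTIs); the SD stays at 4 when capture is incomplete; capture rates are chosen for illustration.

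**Step 1: reproduce the stated power.** Standard error = 4/√100 = 0.4. The two-sided critical value at alpha 0.025 is 2.241. Power = Φ(1.25/0.4 − 2.241) = Φ(0.884) = 0.81; the noncentral t gives 0.80. The stated 81% is reproduced, which supports the paired, two-sided reading.

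**Step 2: baseline under-captured, intervention captured in full, true fall of 1.25.** Observed difference = 6 × (baseline capture) − 4.75.

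| Baseline capture (assumed) | Observed difference | Power, normal | Power, t |
|---|---|---|---|
| 100% | 1.25 | 81% | 80% |
| 95% | 5.70 − 4.75 = 0.95 | 55% | 54% |
| 90% | 5.40 − 4.75 = 0.65 | 27% | 26% |
| 85% | 5.10 − 4.75 = 0.35 | 9% | 9% |
| 80% | 4.80 − 4.75 = 0.05 | 3% | 3% |

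The planned effect disappears at a capture ratio of 4.75/6 = 79%.

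**Step 3: no true effect, unequal capture.** The true mean is 6 in both periods, full capture in one and reduced capture in the other. Spurious difference = 6 × (gap in capture).

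| Gap (assumed) | Spurious difference | Probability of a significant result, t |
|---|---|---|
| none | 0 | 2.5% |
| 5 points | 0.3 | 7% |
| 10 points | 0.6 | 22% |
| 15 points | 0.9 | 49% |
| 20 points | 1.2 | 76% |

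For the 10-point gap the normal approximation gives Φ(0.6/0.4 − 2.241) = Φ(−0.741) = 23%, close to the 22% from t. The sign depends on which period is under-captured. If follow-up captures 90% and baseline 100%, the result is a false fall from 6 to 5.4. If baseline captures 90% and the intervention 100%, it is a false rise from 5.4 to 6.

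These figures show how sensitive the comparison is. They do not show that a gap exists.

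**The case against.** A reader might infer that the plan counts UTIs by different rules in the three periods, and that the letters and weekly contact are verification steps reserved for the intervention. The documents do not support that reading:

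- The criterion given for a verified UTI is antibiotic treatment prescribed by a professional. It requires no letter, urinalysis or culture, and the letters ask for laboratory results that it does not use.
- The weekly contact, as written, is a tablet count and a prompt to complete the USQ-NB. It asks nothing about UTIs or antibiotics.
- The request for results under Medical Information is meant to judge whether the probiotic caused a UTI, not to count UTIs.
- H1 applies the verified count to all three timeframes, so the placement of the definition under Intervention is not itself an asymmetry.
- UTI records, the USQ-NB reminder calls and the H3 antibiotic data are not limited to one period. The USQ-NB items are not reproduced, so the weekly form may already ask about treatment.

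All of this stands, and it reduces the point from a stated difference to an unprotected comparison. It does not remove the point. The statement on UTI records gives no source, interval or method. H3 concerns a different outcome, and a choice between medical records and self-report itself leaves room for capture to vary by period. The USQ-NB is described as a symptom questionnaire, and nothing says that it records prescriptions. Extra contact and a notified provider can also prompt reporting without being formal verification steps.

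A second tempting inference is that any gap would favour the probiotic. If the intervention-only steps do raise capture, the intervention-versus-baseline contrast is biased against it. The direction is unknown.

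**Conclusion.** The point holds as a cheap improvement. The plan leaves the capture of verified UTIs unspecified for baseline and follow-up, and it describes provider letters and weekly tablet-count contact only for the intervention. Equal ascertainment of a co-primary count is therefore not assured in a design with no control arm to absorb a difference. This is a risk left open by silence, not a demonstrated bias.

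The planned effect is a 21% fall (1.25/6), so modest gaps matter: a 10-point shortfall at baseline takes power from 81% to about 27%, and under the null a gap of that size takes the rejection rate from 2.5% to about 22%. These results rest on assumed capture rates, a two-sided test and an SD of change held at 4.

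**What to change.** State one procedure for capturing UTIs and apply it unchanged in all three periods:

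1. With each weekly USQ-NB link, ask whether an antibiotic was prescribed for a UTI that week (yes or no) and on what date. Use the same wording, reminders and phone call throughout.
2. Keep this item outside the count of endorsed USQ-NB items, which is the other co-primary outcome.
3. Apply the same verification step to every positive answer, from the same source and within the same interval.
4. Issue the provider letter at consent rather than at the start of the intervention.
5. Move the definition of a verified UTI to the outcome section, so that it visibly governs all three periods.

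The cost is one extra weekly item, letters sent six months earlier and somewhat more verification work at baseline and follow-up. The change must be in place from the start of baseline, because events missed there cannot be reliably reconstructed. With full and equal capture, the stated power is unchanged.

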Inclusion criteria for participants with SCI/SB/MS includes: 1) age \geq 18 years; 2) SCI/SB/MS; 3) neuropathic bladder at least 1-year duration, as determined by the attending physician; 4) utilizing intermittent catheterization for bladder management; 5) a history of 2 or more UTIs in the past year; 6) community dwelling, 7) Enrollment in Phase II

Exclusion Criteria: Study candidates with the following will be excluded: 1) known genitourinary pathology beyond neuropathic bladder (i.e., vesicoureteral reflux, bladder or kidney stones, etc.); 2) use of prophylactic antibiotics; 3) instillation of intravesicular agents to reduce UTI (i.e., gentamycin); 4) psychologic or psychiatric conditions influencing the ability to follow instructions; 5) participation in another study in which results would be confounded; 6) pregnant or breastfeeding; 7) individuals with a history of acquired or genetic immunodeficiencies; active, acute or chronic serious infections (i.g., viral hepatitis, HIV/AIDS); 8) individuals with cancer/autoimmune disorders; 9) serious allergy to any component or excipients in the live bacterial combination product; 10) no change in neurologic status in the previous 2 weeks; 11) taken antibiotic for any reason in the previous 2 weeks; 12) any patient with history of sensitivity or allergy to ampicillin or tetracycline; and 13) current urinary tract infection or urinary tract infection within the previous 2 weeks (as defined by Infectious Diseases Society of America CAUTI Guidelines, 2010 14) Not enrolled in Phase II. According to the Infectious Disease Society of America Guidelines for Diagnosis of Catheter-Associated UTI, the presence of the

The Impact of Self-Management with Probiotics on Urinary Symptoms and the Urine Microbiome in Individuals with Spinal Cord Injury and Spina Bifida Protocol

5/18/2017

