After 6 months of baseline data collection the intervention phase will begin. Prior to implementing the intervention protocol, participants will provide study staff with a urine sample either at MedStar NRH, CNMC, or when possible, the study RA will meet with the participant at a mutually convenient location. After urine sample is collected, study participants will follow the study protocol and complete USQ-NB weekly. If/when urinary symptoms occur, they will be instructed to follow the SMP_{PRO} protocol to determine whether to initiate intravesicular *Lactobacillus* instillation or be evaluated by a physician. The self-management protocol (SMP_{PRO}) will also direct them to discontinue *Lactobacillus* instillation or be evaluated by a physician if symptoms remit, persist or worsen. If participants are directed by the self-management protocol to seek medical attention or s/he feels the need for medical evaluation, s/he will be advised to obtain care as they typically would by their health care provider. Participants will be supplied with letters to be brought to their health care provider notifying them of the study and requesting sharing of urinalysis and urine culture results with the research team. A verified UTI will include those that resulted in antibiotic treatment by a health care professional. An additional urine sample for metagenomics will either be left with the health care provider for pick up by the research team, brought to the research site, or obtained by the RA at a mutually convenient site. If participant is treating urinary symptoms at home with *Lactobacillus*, a urine sample will be dropped off either at MedStar NRH, CNMC or when possible, the study RA will meet with the participant at a mutually convenient location.

The Impact of Self-Management with Probiotics on Urinary Symptoms and the Urine Microbiome in Individuals with Spinal Cord Injury and Spina Bifida Protocol

5/18/2017

Page 8 of 17

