For the intravesicular *Lactobacillus* instillation, the contents of 1 *Lactobacillus* capsule will be mixed into 45 cc sterile 0.9% saline (adult bladder volume is 450cc, so this amount represents 10% of adult bladder volume). After mixing, study personnel will draw up the 45 cc of the liquid *Lactobacillus* mixture into a 60cc catheter tip syringe and instill via the intermittent catheter. For children volume is based on age (see table on page 4 of protocol). Study participant will recheck symptoms after 24 hrs (valid range 22-30 hrs) following the SMP_{PRO} protocol and either complete another *Lactobacillus* instillation or seek medical attention. If symptoms still persist 4 hrs after second instillation, study participants should seek medical attention.

Post-Intervention Follow-Up:

After completion of the 6-month patient-initiated self-management protocol intervention period, participants will monitor symptoms weekly using the USQ-NB. At the end of follow-up, we will obtain another urine sample from all participants.

Measurements:

In addition to the measurements described in Phase II the following measurements will occur for phase III;

Urine Acquisition: A 50-100 ml urine sample will be collected from each subject for (1) urinalysis and cultivation, and (2) urine microbiome by SMRT sequencing. Urine will be collected from a new, unused intermittent catheter.

Urine Preparation: Collected urine will be immediately placed at 4°C. Within 6 hours, samples will be taken to CNMC for sequencing preparation. At CNMC, urine samples will be centrifuged at 4°C, 5,000 x g for 20 minutes. The supernatant will be aliquoted in 2 ml cryotubes and frozen at -20°C. 10ml PBS will be added to the pellet with the remaining supernatant and then centrifuged (5,000xg) at 4°C for 20 minutes. The pellets and aspirated PBS wash solution will be stored at -20°C. Pellets will later be transferred for DNA isolation and SMRT sequencing.

Urinalysis: Urine samples will be assessed utilizing standard clinical microbiology semiquantitative chemical testing using commercial disposable test strips for glucose, bilirubin, ketone, specific gravity, blood pH, protein, urobilinogen, nitrite, and leukocyte esterase. After centrifuging for 5 minutes, microscopic examination for and quantification of WBCs, RBCs, epithelial cells, yeast, bacteria, *Trichomonas vaginalis*, sperm cells, mucous filaments and crystals will be performed using standard microbial techniques.

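### The instillation instructions contradict each other on whether persistent or worse symptoms allow a second instillation, and on who instils in Phase III

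*Combined protocol and SAP*

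**What the plan says.** **Phase II, Intervention.** Two sentences govern what happens after a first instillation.

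- The first reads "The self-management protocol will also direct them to discontinue" Lactobacillus "instillation or to seek medical attention if symptoms remit, persist or worsen".
- The second sets a recheck at 24 hours (valid range 22-30 hours), carried out under SMP_PRO. The participant then performs another Lactobacillus "instillation or seek medical attention, per the subjects choice".

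A closing sentence adds: "If symptoms still persist 4 hrs after second instillation, study participants are instructed to seek medical attention". In this section participants prepare and instil the product themselves, with sterile technique.

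**Phase III, Intervention.** The same pair of sentences appears with small changes: evaluation by a physician replaces medical attention in the first, and the words on the participant's choice are missing from the second. The preparation paragraph reads "After mixing, study personnel will draw up the 45 cc of the liquid" mixture and has the same staff instil it. It does not mention sterile technique. Earlier in the section, for a participant who is treating symptoms at home with Lactobacillus, "a urine sample will be dropped off either at MedStar NRH, CNMC or when possible" collected by the research assistant at an agreed place.

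**Phase III, Inclusion criteria.** The list ends "community dwelling, 7) Enrollment in Phase II". The exclusion criteria mirror this by excluding anyone not in Phase II.

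**The concern.** These are the working instructions for instilling a live organism into the bladder, mostly at home and unsupervised. A participant whose symptoms persist or worsen at the recheck needs one instruction, and the two sentences give different sets of options. A Phase III participant is told in one place to instil and in another that staff will do it.

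Three things are at stake.

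- **Safety.** When to go on, when to seek care, who handles the product and with what technique should each have one answer.
- **Outcomes.** A verified UTI is one that led to a prescribed antibiotic. The count of verified UTIs is a primary outcome under H1, and antibiotic use is the H3 outcome. Whether an unresolved episode goes to a second instillation or to a prescriber lies on the route to both.
- **Adherence reporting.** The Data and Safety Monitoring Plan requires the DSMB report to cover whether SMP_PRO implementation, instillation and care-seeking were correct. The protocol text should agree with whatever standard is used for that.

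**Working it through.** No sample size, power or event figure is involved, so there is no arithmetic. The check sets the sentences side by side.

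**(a) Action after the first instillation**

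| Sentence | Symptom state named | Stop | Instil again | Seek care |
|---|---|---|---|---|
| Direction sentence, Phase II and Phase III | remit, persist or worsen | listed | not listed | listed |
| Recheck sentence, Phase II and Phase III | none | not listed | listed | listed |

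1. Take the direction sentence at its most charitable: stop if symptoms remit, seek care if they persist or worsen.
2. Apply the recheck sentence to a participant whose symptoms persist or are worse. It permits a second instillation as an alternative to care.
3. The charitable reading therefore does not remove the conflict. For those two symptom states, one sentence leads to care and the other allows re-instillation.
4. One could instead treat the direction sentence as describing the end of the sequence, after the second instillation. The closing sentence, "If symptoms still persist 4 hrs after second instillation, study participants are instructed to seek medical attention", would fit that for persistence. But the direction sentence carries no such timing, and this reading leaves worsening symptoms at the recheck without an instruction of their own.
5. Both phases carry the pair, so the contradiction lies within each phase's own text.

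**(b) Who instils, and how**

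| Source | Who prepares and instils | Sterile technique stated |
|---|---|---|
| Phase II, Intervention | participants | yes |
| Phase III, Intervention, preparation paragraph | study personnel | no |
| Phase III, Intervention, urine-sample sentence | participant treating at home | not addressed |

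1. The Phase III preparation paragraph conflicts with the home-treatment provision in its own section.
2. It also conflicts with the Phase II text.
3. By "community dwelling, 7) Enrollment in Phase II", every Phase III participant is also a Phase II participant. The two texts cannot be separated as rules for different people.

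**The case against.** The strongest reply is that the controlling rule is the SMP_PRO decision tree, whose content is not in these documents. Both Intervention sections refer to SMP_PRO, and the sentences compared here may be loose summaries of it. This stands in part. It cannot be said that the trial has no single rule, only that the protocol's account of it is inconsistent. If the tree settles the matter, the protocol text still has to be brought into line with it.

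On who instils, the Phase III preparation paragraph follows the Phase Ia clinic wording almost exactly. It also keeps a sentence on children's volumes although Phase III enrols adults only. Carried-over text is a plausible explanation, but it remains the stated Phase III instruction.

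A reader might infer more than the documents support:

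- **That resolved symptoms lead to re-dosing or care.** The direction sentence covers stopping on remission, and the word still in "If symptoms still persist 4 hrs after second instillation, study participants are instructed to seek medical attention" implies that the second instillation was meant for unresolved symptoms.
- **That the phases contradict each other on who decides.** Phase III merely omits "per the subjects choice"; it states nothing opposite. A protocol can also direct someone to a point of choice.
- **That the conflict doubles exposure, or touches every treated episode.** One or two instillations is the stated design (the Phase III title says up to 2). On the ordinary reading, only episodes unresolved at the recheck are affected.
- **That the two recheck times conflict.** They follow different instillations.
- **That DSMB adherence scoring is impossible.** The report covers adherence to SMP_PRO, and the unseen tree may give a usable standard.

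**Conclusion.** The point holds in two parts, both wrong as written. First, for symptoms that persist or worsen after the first instillation, the direction sentence does not list re-instillation and the recheck sentence permits it, in both phases. Second, the Phase III preparation paragraph assigns instillation to study personnel and drops the sterile-technique wording, against the Phase II text and against home treatment within Phase III.

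The first part reaches episodes unresolved at the recheck among up to 120 Phase II participants. The documents do not say how many such episodes to expect. The second reaches all 30 Phase III participants. No bias in verified UTIs or antibiotic use has been shown: participants may seek care whenever they feel the need, so neither the direction nor the size of any effect can be derived.

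The conclusion assumes only that the protocol text is meant to be followed as written alongside SMP_PRO. Because these are treatment instructions for home use of a live organism, and because seeking care is a route to a primary outcome, the matter is more than clerical. No view is taken on which clinical rule is right.

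**What to change.** Reconcile the Phase II and Phase III Intervention sections with each other and with the SMP_PRO decision tree, so that one text serves both phases. It should state:

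- the action at the recheck when symptoms persist, and when they are worse;
- whether that action is the participant's choice or is set by SMP_PRO;
- who prepares and instils the product, and with what technique.

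Name that text as the reference for the adherence section of the DSMB report. The investigators decide the content of each rule.

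The cost is protocol wording and matching changes to the SMP_PRO instructions given to participants. No visits, samples or participants are added.
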